Abbreviated Title: CALM Therapy

NIH Protocol #: 000293

Version Date: 06/10/2024

NCT Number: NCT04852302

Title: Managing Cancer and Living Meaningfully (CALM) Therapy in Individuals Diagnosed with a Primary Central Nervous System Tumor

NCI Principal Investigator: [name], RN, FAAN
Neuro-Oncology Branch (NOB)
National Cancer Institute (NCI)
[name]
[name]
[name]
[contact]
[contact]
E-mail: [contact]

Behavioral Intervention: CALM

PRÉCIS

Background:

- Psychological distress is an emotional state experienced by primary central nervous system tumor (PCNST) patients throughout the illness trajectory. It can often be under-identified in this patient population.
- Limited therapeutic interventions in managing distress symptoms can allow symptoms to linger without tailored mechanisms to manage the emotional challenges experienced with a tumor diagnosis. Individualized therapy in advanced cancer patients is a preferred method over pharmacological interventions when managing psychological distress, but more evidence-based research is needed to address the benefits.
- The CALM intervention is a brief, individualized psychotherapeutic intervention established to meet an unmet need to address psychological distress and promote well-being in advanced cancer patients. Previous studies implementing the CALM intervention have focused on metastatic and advanced cancer patients and have reported positive effects. Implementing the CALM intervention in a sample of PCNST patients will be one of the first studies to identify the preliminary effectiveness.

Objective:

- To demonstrate the effects of the CALM intervention in the reduction of depressive symptoms using the PROMIS-Depression scale in PCNST participants, from baseline to 6 months.

Eligibility:

- Adult participants \geq 18 years of age with a PCNST diagnosis who are undergoing standard of care or experimental treatment.
- The ability of the subject to speak English.
- Subjects who have a life expectancy of at least 3 months from time of study entry to allow for participation in the 3 required sessions.
- The ability of the subject to understand and willing to sign a written informed consent document as determined by the assessment of the clinical team.

Design:

- A total of 100 participants may be enrolled

1 INTRODUCTION

1.1 STUDY OBJECTIVES

1.1.1 Primary Objective

- To demonstrate the effects of the CALM intervention in the reduction of depressive symptoms using the PROMIS-Depression scale in PCNST participants, from baseline to 6 months.

1.1.2 Secondary Objectives

- To demonstrate the short-term effects of the CALM intervention in the reduction of depressive symptoms using the PROMIS-Depression scale in PCNST participants from baseline to 3 months.
- To determine the effects of the CALM intervention on death anxiety using the Death and Dying Distress Scale at both 3 and 6 months, compared to baseline.
- To describe the feasibility of implementing CALM remotely in a PCNST population, including eligibility, accrual, compliance, adverse effects, study completion, and participant satisfaction with the intervention.

1.1.3 Exploratory Objectives

- To determine the effects of the CALM intervention on psychological well-being as measured by the Quality of Life Cancer scale (QUAL-EC) and the modified and brief Experiences in Close Relationships (ECR-M-16) questionnaire at both 3 and 6 months, compared to baseline
- To explore the effects of the CALM intervention, more specifically the relationship between distress and symptom burden as measured by the M.D. Anderson Symptom Inventory-Brain tumor (MDASI-BT) for those with brain or brain and spine tumors and the M.D. Anderson Symptom Inventory-Spine Tumor (MDASI-SP) for those with spine tumors, symptom severity and symptom factor scores.
- To explore the effects of the CALM intervention on the relationship between distress and symptom interference as measured by the MDASI-BT or MDASI-SP interference scores.
- To explore the effects of the CALM intervention on health status as measured by the EQ-5D.

1.2 BACKGROUND AND RATIONALE

1.2.1 Psychological distress

Psychological distress is estimated to affect between 30% and 73% of patients with primary malignant brain tumors (1, 2) (3). Limited data exists in the primary spine tumor patient population, but a recent unpublished analysis of data collected as part of the NOB-Natural History Study on 73 patients revealed that 38% reported moderate-severe distress on the M.D. Anderson Symptom Inventory-Spine Tumor (MDASI-SP), and 23% moderate-severe anxiety and 14% moderate-severe depression using PROMIS self-report instruments. Distress is usually under-identified in brain tumor patients (4) (5) and has been found to persist across the illness trajectory (6). Mood disturbance in glioma patients has been found to be similar to breast cancer populations (7). Several

research findings have reported the associations between emotional distress with performance status and psychotropic medication use (8) (9), emotional distress in survivorship (8), symptom burden in minority CNS patients (10), sleep disturbance effects on mood interference (11), increased mood disturbance association with low hope (12), confirming the distress glioma patients experience. The majority of studies in PCNST patients has been cross-sectional or retrospective in nature (13-15), but indicate that depressive symptoms commonly occur in approximately a third of patients. The few longitudinal studies that have been done, indicate that patients remain with symptoms through the follow-up period (3 and 6-month time point)(14, 15).

As the first stage in a research program dedicated to understanding and treating psychological distress in patients with advanced cancer, a Canadian Institutes for Health Research (CIHR)-funded longitudinal, mixed-methods study of patients with metastatic gastrointestinal (GI) and lung cancer, with an expected survival of 12-18 months was completed at Princess Margaret Cancer Centre (PM) (16). Authors identified the prevalence, course, and predictors of depression and demoralization, showing that clinically significant depressive symptoms were present in 27% of the baseline sample (16). Based on cross-sectional and longitudinal evidence, the authors proposed that these symptoms are best understood as a final common ‘pathway of distress’, emerging in response to the interaction of multiple disease-related, individual and psychosocial factors (16-21). The most prominent of these is the physical burden of disease, attachment anxiety (i.e. worry about the availability of supportive relationships and the capacity to make use of them for emotional support), lower self-esteem, hopelessness, and impaired spiritual well-being (16, 19).

Depressive symptoms in cancer patients deserve attention because they are associated with psychological well-being and quality of life (22), noncompliance with medical treatment (23), distress in caregivers (20), and increased health care utilization (24). Unfortunately, depression is often undetected and untreated in cancer and other medical populations (25, 26). Researchers at PM have shown that the majority of patients with metastatic cancer and clinically significant depressive symptoms are not referred for psychosocial care and that most of those referred do not receive specific or adequate treatment for depression (27). Importantly, findings in patients with advanced cancer suggest that psychological treatments for depression are preferred over pharmacological ones (28, 29). Although group therapy has received considerable attention in the literature (30-33), individual psychotherapy is often preferred by patients with advanced disease and is often more feasible to deliver because sessions can be flexibly tailored to patients’ individual needs, taking into account other clinic appointments and fluctuations in health status (34-37).

To address the lack of evidence-based, individual therapies tailored for this population with advanced disease who are earlier in the disease trajectory, the clinical and research team at PM developed a brief, individual psychotherapeutic intervention to alleviate depression and promote psychological well-being. This psychotherapy, designated **CALM** (Managing Cancer And Living Meaningfully) (38), was designed to address the specific problems and risk factors that contribute to the emergence of depressive symptoms in this circumstance (16, 19). CALM provides support and reflective space for the processing of thoughts and emotions evoked by this traumatic condition and facilitates the resolution of practical and existential questions that face individuals with metastatic disease.

1.2.2 CALM Psychotherapy

CALM is a semi-structured, manualized, individual psychotherapy designed for patients with advanced cancer and their loved ones. It shares features with manualized supportive-expressive (30, 39-43), cognitive-existential (44, 45), and meaning-centered (46) group psychotherapies applied to patients with advanced and terminal disease. It was developed based on empirical data, clinical observations, and the theoretical foundations of relational (47), attachment (48), and existential (49) theory. It is informed by Princess Margaret's team CIHR-funded longitudinal research aimed at identifying the antecedents and course of psychosocial morbidity in individuals with metastatic cancer (16-19, 21, 50).

CALM includes 3-6 individual therapy sessions, each approximately 45-60 minutes in length, delivered over 3-6 months. Additional sessions may be offered if clinically indicated while the participant is on the study, with the CALM domains being revisited if the participant is still experiencing challenges and the CALM therapist identifies this need to help the participant process any additional feelings. A maximum of 3 booster sessions will be offered. The sessions cover 4 domains: 1) symptom management and communication with health care providers; 2) changes in self and relations with close others; 3) sense of meaning and purpose, and 4) the future and mortality (38). CALM will be done following the manual that was created by the researchers at Princess Margaret (PM), which is currently in print (51). All modules will be addressed with each patient, but the sequencing and time devoted to each domain will vary, based on the concerns that are most relevant to each patient. The patient's caregiver (e.g., spouse, adult son/daughter, family member), or other persons accompanying the patient are encouraged to participate in one or more of the therapy sessions, as deemed appropriate by the patient and therapist. CALM can be delivered by specially trained therapists from a wide range of disciplines, including social work, nursing, psychiatry, psychology, and medicine (38, 52).

Research conducted over the past decade has shown that CALM is a feasible, acceptable, and effective therapy for patients with advanced or metastatic cancer. In qualitative interviews conducted during the pilot phases of CALM, participants reported that “[CALM] allowed me to express my fears while maintaining my dignity,” “gave me a place to talk openly without having to be positive all the time,” “[allowed me to be] seen as a whole person within the medical system,” diminished fears of taking necessary pain medication or accepting help from others, and “[caused me to be] less afraid of dying.” There was no negative feedback from participants about their experiences of CALM and no withdrawals from treatment based on dissatisfaction with it (53). Additionally, within the feasibility study, patients who completed at least 3 sessions, even with the small sample size and significant attrition, PM researchers found depression and death anxiety, even though small were found to significantly decline over time (54). The randomized controlled trial (RCT) showed that when comparing patients that received the CALM intervention to the Usual Care group, CALM patients reported less severe depressive symptoms at the primary endpoint (3-month), this effect was also greater at the 6-month assessment (55).

This will be one of the first studies utilizing CALM as a telepsychology intervention in a sample of PCNST patients. Common barriers for patients in receiving mental health treatment can include stigma concerns, geographical isolation, time commitments, and transportation. Thus, having the ability to access telepsychology can decrease patient challenges by allowing them the flexibility to be treated in the comfort of one's home, while also optimizing the patient and providers time (56). A recent meta-analysis conducted for depression found no evidence to suggest that the use of synchronous (real-time visual and auditory interactions between patients and

providers) telepsychology was less effective compared to non-telepsychology methods in reducing symptoms (57).

Understanding the effects of CALM using telepsychology in this patient population will help in identifying feasible methods in treating patients' distress and will be used to calculate sample size and effect for a multicenter randomized study, evaluating CALM versus standard of care in the PCNST patient population. This can allow for more tailored psychosocial interventions focused on patients' needs and can provide additional coping mechanisms utilized throughout the illness trajectory in dealing with challenges associated with a PCNST diagnosis.

1.2.3 Questionnaires and Interviews

1.2.3.1 The Patient-Reported Outcomes Measurement Information System (PROMIS)

The PROMIS®-Depression Short Form (version 8a) will be utilized to measure participants' depressive symptoms. This eight-item assessment allows participants to self-report the frequency of depressive symptoms experienced within the past 7 days. Participants are asked to rank symptoms on a scale that includes "never, rarely, sometimes, often and always." PROMIS® has been developed by the U. S. Department of Health and Human Services and is available at no cost (58).

1.2.3.2 The Death and Dying Distress Scale (DADDS)

A validated 15-item scale measuring death anxiety in advanced cancer patients (59) (60). It addresses fears about the dying process and distress about lost opportunities and self-perceived burden placed on others as a result of impending mortality. Scores range from 0-75, higher scores represent greater distress.

1.2.3.3 The modified version of the Clinical Evaluation Questionnaire (CEQ)

This will be used to evaluate the extent to which participants felt supported by their CALM therapist. For this study, 8 items were added to the measure to better capture the extent to which CALM therapy helps participants cope with the future, discuss important things with loved ones, and increase double awareness.

1.2.3.4 CALM Qualitative Interview

A brief, 5-item semi-structured interview was developed by the CALM researchers. Study participants who have completed at least 3 sessions during the course of the study may be asked to complete a qualitative interview. Qualitative interviews will be conducted until thematic saturation is reached (i.e., adequate data has been identified and no new information is expected). Determination of sample size to reach thematic saturation is estimated to be between 15-30 participants (61) (62) (63). The purpose of the interviews is to evaluate participants' overall experience with CALM therapy across each of the four CALM dimensions, the therapeutic alliance, and the structure and timeframe of CALM.

1.2.3.5 The Quality of Life-Cancer Scale (QUAL-EC)

This is a 17-item measure of the quality of life in patient populations near the end of life and includes 4 subscales: Symptom Impact (i.e. list of physical symptoms experienced in the previous month and their frequency, severity, and interference), Preparation for the End-of-Life (i.e., extent to which the family is prepared, financial plans have been made), Relationship with Healthcare Providers (i.e., extent to which patients feel informed, are able to participate in decisions about

their care) and sense of Life Completion (i.e., being able to share important things and to feel connected to others).

1.2.3.6 The modified and brief Experiences in Close Relationships (ECR-M-16)

Attachment insecurities will be assessed using a widely used 16-item measure of attachment security, or the ability to rely on close others for support when distressed, which has demonstrated reliability and validity. It provides subscale scores assessing attachment anxiety (i.e., fear of abandonment) and avoidance (i.e., defensive independence).

1.2.3.7 MDASI-BT or MDASI-SP

This study will use the M.D. Anderson Symptom Inventory-Brain Tumor Module or Spine Tumor Module (MDASI-BT and MDASI-SP, respectively) The MDASI-BT and MDASI-SP have demonstrated reliability and validity in the adult primary brain and spine tumor patient population. This tool represents a modification of the widely used and validated M.D. Anderson Symptom Inventory, with particular attention to symptoms common in patients with brain and spine tumors respectively.

The scales include symptoms rated on an 11-point scale (0 to 10) to indicate the presence and severity of the symptom, with 0 being “not present” and 10 being “as bad as you can imagine.” Each symptom is rated at its worst in the last 24 hours. Symptoms included on the instrument include those commonly associated with cancer therapies, common across cancers and focal neurologic symptoms common in those with either brain or spine tumors. The scales both also includes ratings of how much symptoms interfered with different aspects of a patient’s life in the last 24 hours. These interference items include general activity, mood, work (includes both works outside the home and housework), relations with other people, walking, and enjoyment of life. The interference items are also measured on 0 - 10 scales. The average time to complete either scale is 5 minutes. Both have demonstrated measures of reliability and validity ([64](#), [65](#)).

1.2.3.8 EQ-5D

EQ-5D™ is a standardized instrument for use as a measure of health outcome. Applicable to a wide range of health conditions and treatments, the EQ-5D health questionnaire provides a simple descriptive profile and a single index value for health status. This EQ-5D was developed based on the health status of the community, which are more mobile and have fewer symptoms than the primary central nervous system tumor population.

1.2.3.9 Was It Worth It (WIWI)

The WIWI is a brief questionnaire that is designed to measure a participant’s opinion of their participation. WIWI questions are dichotomous (yes/no) and are tailored to be specific to the intervention involved in the study. For the purposes of this study, there will be four yes/no questions that ascertain the participants’ satisfaction with the CALM intervention.

2 ELIGIBILITY ASSESSMENT AND ENROLLMENT

2.1 ELIGIBILITY CRITERIA

2.1.1 Inclusion Criteria

- Subjects with histological or imaging confirmation of PCNST who are undergoing standard of care or experimental treatment.
- Adults (≥ 18 years of age) who are English-speaking
- Subjects who have a life expectancy of at least 3 months from time of study entry to allow for participation in the 3 required sessions.
- Subjects must be enrolled on the Neuro-Oncology Branch Natural History Study 16C0151.
- The ability of the subject to understand and the willingness to sign a written informed consent document as determined by the assessment of the treating physicians.

2.1.2 Exclusion Criteria

- Participants without access to a smartphone, computer, or tablet to complete remote sessions.

2.1.3 Recruitment Strategies

Participants will be recruited from the Natural History Study (NHS) # 16C0151 by invitation. This protocol may be abstracted into a plain language announcement that will be posted on NIH websites and on NIH social media platforms. Any recruitment materials will be submitted to the IRB for review prior to implementation.

2.2 SCREENING EVALUATION

2.2.1 Screening activities performed prior to obtaining informed consent

Minimal risk activities that may be performed before the subject has signed a consent include the following:

- Email, written, in person or telephone communications with prospective subjects.
- Review of existing medical records to include H&P, laboratory studies, etc.
- Review of existing pathology specimens/reports from a specimen obtained for diagnostic purposes.
- Confirmation of enrollment into NCI protocol “Natural History Study (NCI CC# 16C0151).

2.2.2 Screening activities performed after consent for screening has been signed

No additional screening activities are required.

2.3 PARTICIPANT REGISTRATION AND STATUS UPDATE PROCEDURES

Registration and status updates (e.g., when a participant is taken off protocol therapy and when a participant is taken off-study) will take place per CCR SOP ADCR-2, CCR Participant

Registration & Status Updates found at:
<https://ccrod.cancer.gov/confluence/pages/viewpage.action?pageId=73203825>.

2.3.1 Treatment Assignment Procedures

Cohorts

Number	Name	Description
1	Cohort 1	Participants diagnosed with a primary central nervous system tumor who are undergoing standard of care or experimental treatment.

Arms

Number	Name	Description
1	CALM intervention (remote)	All sessions and patient outcome questionnaires will be completed remotely.

Participants in Cohort 1 will be directly assigned to Arm 1.

2.4 BASELINE EVALUATION

Baseline evaluation will be completed within 14 days prior to CALM therapy initiation unless specified otherwise.

Participants will be asked to complete 6 questionnaires at baseline:

1. PROMIS-Depression,
2. Quality of life (QUAL-EC),
3. Death anxiety (DADDS),
4. Attachment Insecurities (ECR-M-16),
5. Presence and severity of the symptoms (MDASI-BT or MDASI-SP) (within 2 months prior to CALM therapy),
6. Health outcomes (EQ-5D) (within 2 months prior to CALM therapy).

For more details, please, see Section [3.2](#)

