3.4 STUDY CALENDAR

Procedure	Baseline evaluation	CALM Therapy	3-month evaluation (+/- 2 weeks)	6-month evaluation (+/- 2 weeks)
CALM Therapy ¹			→	
Adverse Events			→	
PROMIS-Depression	X		X	X
The Quality of Life at the End of Life-Cancer Scale (QUAL-EC)	X		X	X
The Death and Dying Distress Scale (DADDS)	X		X	X
Experiences in Close Relationships (ECR-M-16)	X		X	X
Clinical Evaluation Questionnaire (CEQ) ⁵			X	X
MDASI-BT or MDASI-SP ²	X		X	
EQ-5D ²	X		X	
Qualitative Interview ^{3,4}		X		
WIWI ⁵			X	X

1. CALM therapy includes 3-6 individual sessions delivered over 6 months. Additional sessions may be offered if clinically indicated while the participant is on the study.
2. Completed within 2 months prior to CALM therapy and any time after the 3rd CALM session while the participant is on the study. If these questionnaires are completed on 16C0151 protocol within the time frames required by this protocol, completion of these questionnaires do not need to be repeated.
3. The Qualitative Interviews will be conducted and scheduled within 1-2 months after participants' 3rd session.
4. The Qualitative Interviews will be conducted on a select number of participants until data saturation is reached (i.e., estimated to be 15-30 patients).
5. The CEQ and WIWI will be completed at 3 months with 6 month completion if more than 3 sessions are completed.

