8.3.3 Exploratory Analyses

To determine the effect of the CALM intervention on well-being, we will calculate effect size differences in well-being using between baseline and months 3 and 6.

To explore the effects of the CALM intervention on symptom burden and interference, we will report subscale scores for the MDASI-BT and MDASI-SP and the proportion of participants with 5 or greater (moderate to severe) and 7 or greater (severe) ratings on the 0-10 numeric rating scale of each symptom items for each time point. To quantify the immediate CALM effect, we will calculate the effect size difference between baseline scores and month 3. To quantify the long term CALM effect, we will calculate the effect size differences between baseline and month 6. We will fit a linear mixed model with participants as a random effect and time as a fixed effect using MDASI-BT and MDASI-SP subscale scores as a dependent variable.

To explore the effects of the CALM intervention on health status, we will perform linear mixed models and effect size calculations on health status using raw and subscale scores from the EQ-5D. To quantify the immediate CALM effect, we will calculate the effect size difference between baseline scores and month 3. To quantify the long-term CALM effect, we will calculate the effect size differences between baseline and month 6. We will fit a linear mixed model with participants as a random effect and time as a fixed effect using EQ-5D as a dependent variable.

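### Baseline MDASI and EQ-5D forms may be up to two months old when CALM starts, so change before therapy enters the exploratory month-3 effect sizes

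*Combined protocol and SAP*

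**What the plan says.** Section 2.4 gives the general rule: "Baseline evaluation will be completed within 14 days prior to CALM therapy initiation unless specified otherwise". PROMIS-Depression, QUAL-EC, DADDS and ECR-M-16 fall under it. Two instruments are exempted by name: "Presence and severity of the symptoms (MDASI-BT or MDASI-SP) (within 2 months prior to CALM therapy") and "Health outcomes (EQ-5D) (within 2 months prior to CALM therapy").

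Footnote 2 of the study calendar (section 3.4) repeats the exemption and also covers the follow-up form: "Completed within 2 months prior to CALM therapy and any time after the 3rd CALM session while the participant is on the study". It then waives repeat completion on this condition: "If these questionnaires are completed on 16C0151 protocol within the time frames required by this protocol". The calendar itself marks MDASI and EQ-5D under the column "3-month evaluation (+/- 2 weeks").

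On recall, section 1.2.3.7 says of the MDASI: "Each symptom is rated at its worst in the last 24 hours".

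Section 8.3.3 then states, for the MDASI and again for the EQ-5D: "To quantify the immediate CALM effect, we will calculate the effect size difference between baseline scores and month 3". The linear mixed models for both name time as the only fixed effect, with participant as a random effect. Section 3.1 describes a single-arm design.

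**The concern.** With no control group, the baseline score is the only reference for change. If the form was completed two months before the first session, the difference to month 3 covers two months without CALM plus the time on CALM, and the analysis credits all of it to CALM. Because the MDASI asks about the last 24 hours, an old form says nothing about the weeks between its completion and the first session.

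Change in that gap is plausible. The inclusion criteria (section 2.1.1) describe patients undergoing standard or experimental treatment, section 6.1 records whether disease at entry is newly diagnosed, recurrent or under surveillance, and the life-expectancy criterion is only 3 months. The bias could go either way: worsening before therapy would hide a benefit, and recovery before therapy would imitate one.

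At stake are the exploratory MDASI and EQ-5D effect sizes and the time term in their mixed models. Section 1.2.2 says the study's results will be used to size a later randomised trial, so effect sizes reported from these instruments may be read in that light.

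**Working it through.** The plan gives no figure for this point (no sample size, power or allowance for baseline age for MDASI or EQ-5D), so there is nothing to reproduce first.

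**Inputs**
- Baseline age, MDASI and EQ-5D: up to 2 months (section 2.4; calendar footnote 2).
- Baseline age, other questionnaires: up to 14 days (section 2.4). At 30.4375 days per month, 14/30.4375 = 0.46 month.
- Follow-up: 3 months, plus or minus 2 weeks (section 3.4).
- Assumption: month 3 is counted from the start of therapy. The documents do not state the origin.

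**Share of elapsed time before therapy** = baseline age / (baseline age + time from therapy start to follow-up)

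| Follow-up | Baseline 2 months old | Baseline 14 days old |
|---|---|---|
| 3 months | 2/(2+3) = 40.0% | 0.46/(0.46+3) = 13.3% |
| 3 months minus 2 weeks | 2/(2+2.54) = 44.1% | 0.46/(0.46+2.54) = 15.3% |
| 3 months plus 2 weeks | 2/(2+3.46) = 36.6% | 0.46/(0.46+3.46) = 11.7% |

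**Sensitivity to what the documents leave open**
- If month 3 is instead counted from the baseline form, the share for a 2-month-old form is 2/3 = 66.7%.
- Footnote 2 does not tie the follow-up form to month 3. With assumed follow-up at 1 month after therapy start the share is 2/(2+1) = 66.7%; at 2 months it is 2/(2+2) = 50.0%. A follow-up later than month 3 gives less than 40%.

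So 40% is the nominal case and not an upper limit.

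**From time to change.** Let the score move by *a* per month before therapy and by *b* per month afterwards. The pre-therapy share of the total change is then 2a/(2a+3b).
- a = 1, b = 1: 2/5 = 40%
- a = 1, b = 0.5: 2/3.5 = 57%
- a = 1, b = 0: 2/2 = 100%
- a = 0, b = 1: 0/3 = 0%

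The share of change equals the share of time only when the rate is the same before and after therapy starts. The documents give neither *a* nor *b*, so the share of change cannot be stated.

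**The case against.** The strongest defence is that the window is a deliberate trade-off, stated the same way in section 2.4 and in the calendar footnote. Every participant is enrolled on 16C0151, the questionnaire set already takes 40-60 minutes (section 3.2), and reusing an existing form spares burden and may help the 80% compliance criterion in section 8.3.2. This stands: the two windows do not contradict each other. It does not answer the analysis, which makes no allowance for an older baseline.

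A second defence is that tightening the window gains little, because in a single-arm study change after therapy starts cannot be attributed to CALM either. This also stands as a limit on the fix. Still, change before the first session cannot be due to CALM at all, and that part can be largely removed.

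A third is scope. MDASI and EQ-5D are exploratory, with no powered hypothesis and no stopping rule. PROMIS-Depression (primary) and DADDS (secondary) already have the 14-day baseline. The figures above are also worst cases, since nothing shows how many participants would have a form near two months old. All of this stands and sets the weight of the point.

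Stronger readings that the documents do not support:
- *That 40% of the observed change predates CALM.* The 40% is elapsed time; no drift rate is given.
- *That distress and symptom scores taken up to two months apart will be analysed together.* The exploratory objectives speak of a relationship between distress and symptoms, but they do not name the distress measure, and section 8.3.3 specifies no model that pairs PROMIS-Depression with the MDASI.
- *That a corresponding share can be quoted for month 6.* Section 3.2 lists these forms at 6 months and section 8.3.3 plans month-6 effect sizes, but the calendar marks no 6-month MDASI or EQ-5D.
- *That the section 3.1 remark on recurrence establishes drift in MDASI scores.* It names depression, distress and quality of life, in support of the enrolment mix.

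**Conclusion.** The point holds as a cheap improvement confined to exploratory endpoints. Followed as written, the plan counts up to two months of pre-therapy change in MDASI and EQ-5D as part of the immediate CALM effect. Counting month 3 from the start of therapy, the pre-therapy period can be about 40% of the elapsed interval, or 44% at the early edge of the visit window, against about 13% (15% at the early edge) with a 14-day baseline. How much of the change this represents is unknown. The primary and death-anxiety results are not touched. A 14-day window would reduce this bias, but it would not turn an uncontrolled difference into a CALM effect.

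**What to change.** 1. In section 2.4 and calendar footnote 2, require the baseline MDASI-BT or MDASI-SP and the EQ-5D within 14 days before the first session, sent in the same survey link as the PROMIS baseline. Accept a 16C0151 form in their place only if it is dated within those 14 days.
2. For participants already enrolled with older forms, report the age of the baseline form and repeat the MDASI and EQ-5D effect sizes restricted to baselines within 14 days.
3. Reconcile the open follow-up timing in footnote 2 with the month-3 analysis in section 8.3.3, and state the origin from which month 3 is counted. Without this, the interval stays uncontrolled at its other end.

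Cost: a small amendment, fewer reused 16C0151 forms, and for some participants about 5 minutes of MDASI (the time given in section 1.2.3.7) plus the EQ-5D, added to a baseline survey they already receive. The restricted analysis in step 2 will have fewer participants and less precision.
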